	Hematologic improvement in erythroid response (HI-E) per IWG (Cheson, 2006)	Proportion of subjects achieving HI-E over any consecutive 56-day period in the absence of RBC transfusions	W1D1 through Week 48
	Time to HI-E	Time from first dose to first onset of achieving ≥ 1.5 g/dL increase in hemoglobin over any consecutive 56-day period in the absence of RBC transfusions	W1D1 through Week 24; W1D1 through Week 48
	Time to mHI-E	Time from first dose to first onset of achieving ≥ 1.5 g/dL mean increase in Hgb compared to baseline over any consecutive 56-day period in the absence of RBC transfusions	W1D1 through Week 24; W1D1 through Week 48
	Duration of HI-E	Maximum duration of achieving ≥ 1.5 g/dL increase in hemoglobin for subjects who achieve Hgb increase ≥ 56 days in the absence of RBC transfusions	W1D1 through EOT
	Duration of mHI-E	Maximum duration of achieving ≥ 1.5 g/dL mean increase in Hgb compared to baseline for subjects who achieve mean Hgb increase ≥ 56 days in the absence of RBC transfusions	W1D1 through EOT
	RBC-TI	Proportion of subjects who maintain RBC-TI from W1D1 through Week 24, 48, and 72.	W1D1 through Week 24; W1D1 through Week 48; W1D1 through Week 72
	Safety	Type, frequency, severity of AEs and relationship of AEs to luspatercept	Screening through 42 days post last dose
	PK	C_{\max} , AUC, T_{\max}	W1D1 through 1-year post first dose

Table 2: Study Endpoints (Continued)

Endpoint	Name	Description	Timeframe
Secondary	Antidrug antibodies (ADA)	Frequency of antidrug antibodies and effects on efficacy, or safety, or PK	W1D1 through 1-year post first dose
	Progression to AML	Number and percentage of subjects progressing to AML; time to AML progression	W1D1 through 5 years from first dose or 3 years from last dose (whichever occurs later)
	Overall survival	Time from date of W1D1 to death due to any cause	W1D1 through 5 years from first dose or 3 years from last dose (whichever occurs later)
Exploratory	Molecular and cellular markers in the bone marrow and/or in peripheral blood	Evaluation of biomarkers that may potentially impact luspatercept efficacy, predict response or relapse, help to better understand MOA and/or provide further prognostic classification of MDS subtypes. Molecular markers (eg, SF3B1) include evaluation of MDS-associated gene mutations and their impact on drug efficacy, clinical response or relapse, disease progression, drug MOA and prognostication of MDS.	Baseline through End of Treatment

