9.6.2. Secondary Efficacy Analyses

The secondary variables will be analyzed descriptively, unless otherwise specified, and will be based on the ITT population and EE population. Kaplan-Meier methods will be used to estimate curves for time to event secondary variables. Counts and percentages will be used to describe categorical variables. Response rate of HI-E per IWG ([Cheson, 2006](#)) within 24 weeks, based on the EE population, will be analyzed as a secondary endpoint.

Modified hematologic improvement - erythroid (mHI-E) per IWG ([Cheson, 2006](#)) is defined as proportion of subjects meeting mHI-E criteria of ≥ 1.5 g/dL mean increase in Hgb compared to baseline that is sustained over any consecutive 56-day period in the absence of RBC

transfusions from W1D1 through Week 24 (and W1D1 through Week 48) of the Treatment Period. Subjects discontinued from the Treatment Period without achieving a mean Hgb increase ≥ 1.5 g/dL will be counted as non-responders.

HI-E per IWG (Cheson, 2006) within 48 weeks is defined as proportion of subjects meeting HI-E criteria of ≥ 1.5 g/dL increase in Hgb sustained over any consecutive 56-day period in the absence of RBC transfusions from W1D1 through Week 48 of the Treatment Period. Subjects discontinued from the Treatment Period without achieving HI-E will be counted as non-responders.

For subjects who have a dose delay meeting the dose modification criterion described in Section 9.6.1, if their Hgb levels temporarily decrease to < 1.5 g/dL but achieve ≥ 1.5 g/dL again after treatment resumption, this period (ie, the time from dose delay to achieving a Hgb increase of ≥ 1.5 g/dL again) will be included as the period of sustained Hgb increase of ≥ 1.5 g/dL.

Time to HI-E will be summarized only for subjects who achieve HI-E. It is defined as time from W1D1 to first onset of achieving ≥ 1.5 g/dL increase in Hgb over any consecutive 56-day period in the absence of RBC transfusions. It will be summarized separately for subjects who achieve HI-E within the first 24 weeks and 48 weeks from W1D1, respectively.

Time to mHI-E will be summarized only for subjects who achieve mHI-E. It is defined as the time from W1D1 to first onset of achieving ≥ 1.5 g/dL mean increase in Hgb over any consecutive 56-day period in the absence of RBC transfusions. It will be summarized separately for subjects who achieve mHI-E within the first 24 weeks and 48 weeks from W1D1, respectively.

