Duration of HI-E will be determined only for subjects who achieve HI-E during the Treatment Period. Duration of HI-E is defined as the maximum duration of achieving ≥ 1.5 g/dL increase in Hgb for subjects who achieve Hgb increase ≥ 56 days in the absence of RBC transfusions. Subjects who maintain HI-E through the end of the Treatment Period or time of analysis will be censored at the date of treatment discontinuation/time of analysis or death, whichever occurs first.

Duration of mHI-E will be determined only for subjects who achieve mHI-E during the Treatment Period. Duration of mHI-E is defined as the maximum duration of achieving ≥ 1.5 g/dL mean increase in Hgb for subjects who achieve a mean Hgb increase of ≥ 56 days in the absence of RBC transfusions. Subjects who maintain mHI-E through the end of the Treatment Period or time of analysis will be censored at the date of treatment discontinuation/time of analysis or death, whichever occurs first.

Proportion of subjects who maintain RBC-TI is defined as proportion of subjects not being given any RBC transfusion during the Treatment Period and will be calculated at Week 24, Week 48, and Week 72.

Time to progression to AML is defined as the time between W1D1 and first diagnosis of AML as per WHO classification of $\geq 20\%$ blasts in peripheral blood or bone marrow. Subjects with diagnosis of AML will be considered to have had an event. Subjects who have not progressed to AML at the time of analysis will be censored at the last assessment date which does not indicate progression to AML.

Overall survival (OS) is defined as the time between W1D1 and death/censored date. Subjects who die, regardless of the cause of death, will be considered to have had an event. Subjects who are alive at the time of analysis will be censored at the last assessment date at which the subject was known to be alive. All subjects who were lost to follow-up will also be censored at the time of last contact.

Full analysis details will be included in the SAP.

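### Duration of HI-E and mHI-E censors responders who die, or stop for worsening disease, while still in response, so the Kaplan-Meier duration can read longer than one counting them as failures

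*Combined protocol and SAP*

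**What the plan says.** Section 9.6.2 restricts both duration endpoints to responders and uses the longest spell: "Duration of HI-E is defined as the maximum duration of achieving" the required rise, with parallel wording for mHI-E. Table 2 in Section 2 says the same: "Maximum duration of achieving ≥ 1.5 g/dL increase in hemoglobin".

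The censoring rule covers "Subjects who maintain HI-E through the end of the Treatment Period or time of analysis". These subjects "will be censored at the date of treatment discontinuation/time of analysis or death, whichever occurs first". The mHI-E rule is the same. No reason for discontinuation is treated differently.

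The section also states that "Kaplan-Meier methods will be used to estimate curves for time to event secondary variables". Duration is not named there, but a censoring rule implies that method. On status, it says "The secondary variables will be analyzed descriptively, unless otherwise specified".

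The only sensitivity analysis described (Section 9.6.1) concerns haemoglobin dips during dose delays for high haemoglobin, under the primary endpoint. Further detail is deferred to the SAP. No separate SAP text is in the document reviewed.

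**The concern.** Kaplan-Meier treats a censored subject as having the same prospects as those still at risk. That is hard to defend for two groups.

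- **Deaths in response.** The response is over, yet the subject is handled as if it might have continued.
- **Stops for worsening disease in response.** Section 6.4.2 requires both clinical benefit and absence of progression to stay on treatment, so a subject with a maintained haemoglobin rise must stop if marrow blasts meet the Appendix E criterion. Table 5 in Section 7.2.2 requires discontinuation for centrally confirmed peripheral blasts of 1% or more, with no haemoglobin condition.

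At stake is how durability is described. Section 1.3.1 looks for benefit over a sustained period, Section 1.1.1.1 quotes response durations for the two erythropoiesis-stimulating agents, and Section 1.3.2.2 says mHI-E was added to allow better comparison with darbepoetin.

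**Working it through.** **1. The plan's own figure.** No figure is stated for duration. The design figure in Section 9.3 is 95% power with N = 20, null 10%, alternative 45%, one-sided 0.025. By the exact binomial, P(X ≥ 5 | 0.10) = 0.0432, which is too large, and P(X ≥ 6 | 0.10) = 0.0113. The critical value is 6, and power is P(X ≥ 6 | 0.45) = 94.5%, which agrees. Expected responders: 20 × 0.45 = 9.

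**2. Who is treated differently.**

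| What happens to a responder | Plan | Failure rule |
|---|---|---|
| Loses the rise, or is transfused, on treatment | event | event |
| Still in response at the data cut | censored | censored |
| Dies in response | censored | event |
| Stops in response for progression or AML | censored | event |
| Stops in response for another reason | censored | censored |

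**3. Direction.** The Kaplan-Meier curve is a product of factors (1 − events/at risk). Relabelling an event as censored removes a factor below 1 and leaves the other risk sets unchanged. The plan's curve is therefore never below the failure-rule curve.

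**4. Nine responders.** If all nine times are events, survival after the fifth is 4/9 = 0.444, so the median is the fifth time. If the third is censored instead:
- after the second: 7/9
- after the fifth: 7/9 × 5/6 × 4/5 = 0.519
- after the sixth: 0.519 × 3/4 = 0.389

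One relabelled subject moves the median from the fifth time to the sixth.

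**5. Deaths only.** Inputs: 56-day minimum response (Section 9.6.1); 197-day median (epoetin alfa study, Section 1.1.1.1); median survivals from Appendix C. Assume a response lasts 56 days plus an exponential time, with constant, independent hazards. Then median = 56 + 1/(1/a + 1/b), where a = 197 − 56 = 141 days and b is median survival in days (years × 365.25).

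| Median survival | b | Time to loss or death | Shorter than 197 by |
|---|---|---|---|
| 8.8 y | 3,214 | 56 + 135.1 = 191 | 3% |
| 5.3 y | 1,936 | 56 + 131.4 = 187 | 5% |
| 3.0 y | 1,096 | 56 + 124.9 = 181 | 8% |

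On an assumed 336-day scale (a = 280) the results are 314, 301 and 279 days.

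**6. Discontinuation in response, rate assumed.** At 20% a year and 5.3-year survival, the summed hazard is ln2/141 + ln2/1,936 − ln(0.8)/365.25 = 0.00492 + 0.00036 + 0.00061 = 0.00589 per day. The median is 56 + 0.693/0.00589 = 174 days (257 on the 336-day scale). Over 0–40% a year and the three survivals, the range is 156–191 days (210–314). These figures count every in-response stop as failure, so they overstate the effect of progression and AML alone.

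**7. Informative stopping, share assumed.** If 20% of losses are pre-empted by stopping just before, the visible loss hazard falls to 0.8 of its value. The plan's median becomes 56 + 141/0.8 = 232 days (233 by simulation) when the true median is 197. On the longer scale it is 56 + 280/0.8 = 406 (407 by simulation) against 336.

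**8. Small samples.** In 5,000 simulated trials of 9 responders (336-day scale, 5.3-year survival, 20% a year stopping, 2-year cut-off, no second episodes), the plan's median was never below the one counting death and all stops as failure. It was higher in 74% of trials. It was not reached in 6.4%, against 0.2%.

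**The case against.** The rule is narrower than it looks. Only subjects still in response are censored; losing the rise or being transfused is an event. Under Section 6.4.2, transfusion independence alone satisfies the clinical-benefit criterion, so a subject who loses HI-E can stay on drug and the loss is observed. Appendix E progression through transfusion dependence has already ended the response. This stands, and it means only some discontinuations matter.

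A reader might infer that the planned durations are biased upward as such. The documents do not support that. If stopping is unrelated to impending loss, Kaplan-Meier correctly estimates on-treatment time to loss: with independent stopping and no second episodes, simulation returned 197 against 197 days and 335 against 336. Step 5 compares two different quantities, and step 7 rests on a share that the protocol does not give.

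A reader might also apply the death hazard from onset. That gives 1/(1/197 + 1/b) = 186, 179 and 167 days, or 6%, 9% and 15% shorter. It ignores that everyone in this analysis has already held a response for 56 days. The inputs are borrowed as well: 197 days comes from another drug in a population that included transfused patients, and Appendix C describes risk categories in general.

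A third tempting inference is that taking the longest episode is an error. It is the declared endpoint in Table 2 and Section 9.6.2, and it need not match time to first onset, which answers another question. If 25–50% of responders had a second episode, the 197-day median would read 220–242, but no such rate is documented.

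Finally, the endpoints are descriptive, and survival and AML progression are reported separately. That limits the harm but leaves the censoring rule as written.

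**Conclusion.** The point holds in a limited form. Section 9.6.2 censors in-response deaths and in-response stops for worsening disease, and the protocol's own rules force some of those stops. The resulting duration cannot be shorter than one that counts them as failures, and is biased for time to loss only if stopping is informative. That is plausible for stops triggered by blasts, but the documents do not quantify it.

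For deaths alone the illustrative effect is 3% to 8% on the 197-day scale, assuming constant independent hazards, the 56-day minimum and the Appendix C survivals. The part due to discontinuation is unknown. With about 9 responders, the practical risk is a median that shifts or is not reached because of one or two subjects. The longest-episode definition is a choice, not a fault. No decision rule or sample size depends on duration. This is an optional, inexpensive improvement, and the SAP may already deal with it.

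**What to change.** In Section 9.6.2, or in the SAP:

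- Add an analysis of duration of HI-E and of mHI-E in which death and discontinuation for disease progression or AML count as end of response. Censor other ongoing responders at their last haemoglobin assessment.
- Report it beside the current censor-at-discontinuation version, and say what each one estimates.
- Tabulate censored responders by reason.
- State which recorded reasons count as progression or AML. Section 11.1 files stops under the dose-modification rules as Other and has no separate entry for AML, so a rule keyed to the disease-progression code alone could miss the peripheral-blast stops.
- Keep the longest-episode definition as declared. A first-episode summary is optional.

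The data are already collected: reason for discontinuation (Sections 6.2.2 and 11.1), and AML and date and cause of death (Section 6.3.2). The cost is some SAP wording, one extra run and a slightly shorter reported median. The primary test and the sample size do not change.

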An antidrug antibodies (ADA) sample(s) may be required in the Post-Treatment Follow-up Period for subjects, who terminate the Treatment Period with less than 1 year of ADA monitoring if a subject is ADA positive at the time of treatment discontinuation.

The study will be conducted in compliance with International Council for Harmonisation (ICH) Good Clinical Practices (GCP).

Study Population

Adult subjects (≥ 20 years) with anemia due to a IPSS-R very low, low, or intermediate risk MDS according to the WHO 2016 classification and a bone marrow blast count of $< 5\%$ ([Arber, 2016](#); [Greenberg, 2012](#)), who are not requiring RBC transfusion (ie, no RBC transfusion administered within 16 weeks prior to W1D1 - except transfusions due to blood loss or infection that occurred between 16 and 8 weeks prior to W1D1), and ESAs naïve or previously used ESAs but not administered ESAs within 8 weeks prior to W1D1.

Length of Study

The expected duration of the study is approximately 8 years, which consists of approximately 2 years of enrollment, approximately 1 additional year of luspatercept treatment after the last subject is enrolled, and 5 years of follow up from first dose of IP, or 3 years from last dose (whichever occurs later), to complete the Post-Treatment Follow-up Period.

The End of Trial is defined as either the date of the last visit of the last subject to complete the post-treatment follow-up, or the date of receipt of the last data point from the last subject that is required for primary, secondary and/or exploratory analysis, as prespecified in the protocol, whichever is the later date.

The sponsor may end the trial when all key endpoints and objectives of the study have been analyzed and the availability of a roll-over protocol exists into which subjects remaining on study may be consented and continue to receive access to luspatercept and/or complete long-term follow-up. Such a protocol would be written for a compound that would not yet be commercially available.

Study Treatments

Eligible subjects will be administered luspatercept (ACE-536): starting dose of 1.0 mg/kg subcutaneous injection every 3 weeks (21 days; Q3W). Dose levels can be increased in a stepwise manner beyond the starting dose to 1.33 mg/kg, and up to a maximum of 1.75 mg/kg.

For a detailed description of study treatments please refer to Section [7](#).

Overview of Key Efficacy Assessments

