The primary efficacy endpoint of HI-E per IWG (Cheson, 2006) is defined as proportion of subjects meeting HI-E criteria of ≥ 1.5 g/dL increase in Hgb sustained over any consecutive 56-day period in the absence of RBC transfusions from W1D1 through Week 24. Subjects discontinued from the treatment period without achieving HI-E will be counted as non-responders. Dose modification guidance for luspatercept in Section 7.2.2 defines that, if predose Hgb is ≥ 12.0 g/dL at the day of dosing, the dose should be delayed until Hgb is < 11.0 g/dL. For subjects who meet this criterion and then have their dose delayed, if their Hgb levels temporarily decrease to < 1.5 g/dL but achieve ≥ 1.5 g/dL again after treatment resumption, this period (ie, the time from dose delay to achieving a Hgb increase of ≥ 1.5 g/dL again) will be included as the period of sustained Hgb increase of ≥ 1.5 g/dL.

As the primary efficacy analysis, one sample binomial one sided exact test will be performed based on intent-to-treat (ITT) population, to provide p-value (significance level: 0.025). The number and percentage of subjects who achieve the response and 95% confidence interval (CI) will be presented based on the ITT population.

There is no planned interim analysis for this study.

The primary analysis will be performed when all enrolled subjects have completed 24 weeks of treatment or discontinued before 24 weeks.

Additional follow-up analysis for efficacy and safety will be performed when all subjects have been followed for 5 years from the date of the first dose of IP, or 3 years from the last dose (whichever occurs later) during the Post-Treatment Follow-Up Period of the study.

For more details on statistical considerations please refer to Section 9 of the protocol.

TABLE OF CONTENTS

TITLE PAGE	1
PROTOCOL SUMMARY	6
TABLE OF CONTENTS	12
LIST OF TABLES	18
LIST OF FIGURES	19
1. INTRODUCTION	20
1.1. Myelodysplastic Syndromes	20
1.1.1. Current Treatment Options for Lower Risk MDS.....	21
1.1.1.1. Erythropoiesis Stimulating Agents.....	21
1.1.1.2. Red Blood Cell Transfusions	22
1.1.1.3. Lenalidomide.....	23
1.1.1.4. Hypomethylating Agents	23
1.2. Luspatercept Background	23
1.2.1. Mechanism of Action	23
1.2.2. Nonclinical Studies with Luspatercept	25
1.2.3. Summary of Clinical Experience	25
1.2.3.1. Potential Risks of Human Use	26
1.2.3.2. Overall Benefit Risk Assessment	27
1.3. Rationale	27
1.3.1. Study Rationale and Purpose	27
1.3.2. Rationale for the Study Design	28

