9.2. Study Population Definitions

Study populations to be analyzed are defined as follows:

Intent-to-treat (ITT): The ITT population will consist of all enrolled subjects regardless of whether or not the subject received IP.

Efficacy Evaluable (EE): The EE population will consist of 1) all subjects who received at least one dose of IP and 2) have at least two hemoglobin assessments \geq 8 weeks apart post-treatment.

Safety: The safety population will consist of all subjects who were enrolled and received at least one dose of IP. Statistical methods to handle missing data will be described in the statistical analysis plan (SAP). The SAP will describe any predefined rules for including/excluding any subjects with data from any analyses (eg, time windows, visit by visit analysis, endpoint analysis, protocol violation).

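### Section 9.6.2 defines maintained RBC transfusion independence over each subject's own Treatment Period instead of Table 2's fixed windows, so subjects can be misclassified at Weeks 24, 48 and 72

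*Combined protocol and SAP*

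**What the plan says.** Table 2 (Section 2) describes the endpoint as "Proportion of subjects who maintain RBC-TI from W1D1 through Week 24, 48, and 72", with a timeframe starting at W1D1 for each landmark. Section 9.6.2 describes it as the "proportion of subjects not being given any RBC transfusion during the Treatment Period and will be calculated at Week 24, Week 48, and Week 72".

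The Treatment Period is not a common length. Under Section 3.1 it runs at least to Day 169 unless the subject stops earlier, and then for as long as the benefit and non-progression criteria are met. Under Section 6.4.1, transfusions are recorded until 8 weeks after the last dose or the EOT visit, whichever is later.

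Secondary variables "will be based on the ITT population and EE population". Section 9.2 adds: "The ITT population will consist of all enrolled subjects regardless of whether or not the subject received IP".

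Other endpoints have explicit rules for incomplete follow-up. For HI-E, "Subjects discontinued from the Treatment Period without achieving HI-E will be counted as non-responders"; mHI-E has a parallel sentence. Duration of HI-E and mHI-E, time to AML and overall survival have censoring rules. RBC-TI has neither kind of rule. Section 9.2 leaves missing-data methods to the SAP, and Section 9.6.2 closes by leaving full analysis details to it as well.

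**The concern.** The two definitions can classify the same subject differently. Three cases show this:

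- **Stops at Week 10 untransfused, including by death.** There was no transfusion in the Treatment Period, so Section 9.6.2 counts the subject as maintaining RBC-TI at Week 72. Transfusion recording has ended long before then.
- **Enrolled but never dosed.** The subject is in the ITT denominator and has no Treatment Period in which to be transfused, so counts as maintained by default.
- **First transfused at Week 60 while still on treatment.** Table 2 counts this subject as maintained at Weeks 24 and 48. Taken literally, Section 9.6.2 fails the subject at all three landmarks.

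Avoiding transfusion dependence is part of the stated therapeutic goal (Sections 1.3.2.1 and 1.3.2.2), and RBC-TI is the only landmark efficacy endpoint reported at Week 72. In a single arm of about 20 subjects, a few such cases visibly change the reported rate. If the rule is settled only after the data are seen, the choice is open to question.

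**Working it through.** **The plan's own figure.** The documents state no expected value for RBC-TI. The only powered figure is for HI-E: N = 20, null 10%, expected 45%, one-sided alpha 0.025, power 95% (Section 9.3). The exact binomial rule is 6 or more responders of 20, with alpha 0.0113 and power 94.5%, so the figure reproduces. RBC-TI does not enter it.

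**Sign of the error.** At landmark X, let s be the subjects who stopped untransfused before X or were never dosed. Let l be those observed transfusion-free to X but first transfused later on treatment.

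- The whole-period rate counts everyone never transfused on treatment. It includes s and excludes l.
- The Table 2 window with observation to X required includes l and excludes s.
- Difference = (s − l)/20, or 5 × (s − l) percentage points.

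The documents give neither s nor l, so the sign is open. For example, s = 3 with l = 1 gives +10 points, and s = 3 with l = 5 gives −10 points.

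**Each direction alone (assumed counts, N = 20, 4 transfused by the landmark).**

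- Upward, with 2 untransfused stoppers, 1 undosed subject and no later transfusions: the literal rate is (20 − 4)/20 = 16/20 = 80% (exact 95% CI 56–94). Observed to the landmark it is (20 − 4 − 3)/20 = 13/20 = 65% (41–85).
- Downward at Week 24, with no early stoppers and 1 to 5 further subjects first transfused later: the whole-period rate is 15/20 = 75% down to 11/20 = 55%. Table 2's window gives 16/20 = 80%.

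**Why a Kaplan-Meier estimate is needed too.** Assume independent exponential times, with 10–30% stopping untransfused and 30–50% first transfused by Week 72. With stopping hazard a and transfusion hazard b:

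- Observed to landmark: N = exp(−(a + b)X)
- Kaplan-Meier target: K = exp(−bX)
- Mixed reading (transfusions counted only up to X, but no observation to X required): L = N + [a/(a + b)] × (1 − N)

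At Week 72 with 30% stopping and 30% transfused, N = 0.70 × 0.70 = 49.0%, K = 70.0% and L = 49.0 + 0.5 × 51.0 = 74.5%. Over the full assumed range, in percentage points:

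| Landmark | K − N | L − K |
|---|---|---|
| Week 24 | 2.7–10.0 | 0.2–1.1 |
| Week 48 | 4.3–16.7 | 0.7–3.8 |
| Week 72 | 5.0–21.0 | 1.4–7.1 |

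So the observed-to-landmark proportion is a conservative lower bound and should not stand alone.

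**The case against.** **The window is already stated.** Table 2 gives it, and calculating the rate at a given week can be read as limiting the count to that week. This is fair, and on that reading the Week 60 case resolves. The untransfused early stopper and the undosed subject do not, because Table 2 has no rule for them either.

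**The SAP will settle it.** This stands as a limit. The absence of a rule is shown for the protocol only. The two protocol definitions still differ and should agree.

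**The cases may be few.** Remaining transfusion-independent is itself one route to continuing treatment (Section 3.1). Enrolment follows confirmed eligibility with dosing within 3 days, and the EE analysis removes undosed subjects. All of this lowers the likely size. Untransfused subjects can nevertheless stop for adverse events, withdrawal, progression or death (Section 11.1).

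**Counting every early stopper as a failure would be worse.** This stands. Under the assumptions above, that proportion lies further from Kaplan-Meier than the mixed reading does. It would also fail subjects whose treatment ends administratively: the Protocol Summary foresees about 1 year of treatment after the last enrolment, which is shorter than 72 weeks.

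Two stronger readings are tempting but unsupported. A reader might infer that the wording necessarily inflates RBC-TI and that correcting it must lower the reported rates. That follows only under the mixed reading; under the whole-period reading later transfusions pull the other way. A reader might also infer that many subjects will be short of Week 48 or 72 when rates are reported, because "The primary analysis will be performed when all enrolled subjects have completed 24 weeks of treatment or discontinued before 24 weeks". Nothing schedules those later rates for that analysis. The Protocol Summary also plans a further efficacy analysis after long-term follow-up, when every subject is past Week 72 in calendar time.

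**Conclusion.** The point holds as a minor definitional defect in the protocol. Followed as written on the ITT population, Section 9.6.2 credits subjects with transfusion independence at landmarks they did not reach and can fail subjects who met Table 2's definition. This goes beyond missing detail, because the stated rule itself misclassifies.

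The size is 5 percentage points per misclassified subject, assuming 20 ITT subjects. The net direction cannot be determined from the documents. The illustrative counts, and the stopping and transfusion rates, are assumptions; the documents give none. No hypothesis test or decision rule depends on this endpoint.

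**What to change.** In Section 9.6.2:

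1. Define RBC-TI as no RBC transfusion from W1D1 through Week 24, 48 or 72, as in Table 2. Count a subject as maintaining it only if observed transfusion-free to that landmark.
2. In the ITT table, show as separate categories, not as maintained, subjects who stopped untransfused before the landmark, were never dosed, or ended treatment administratively.
3. Add a Kaplan-Meier estimate of time to first RBC transfusion at the three landmarks. State that it assumes non-informative stopping and excludes undosed subjects, who have no W1D1.

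Carry the same wording into the SAP. The cost is a text change and one extra descriptive analysis of data already collected. The headline proportion may come out lower, which is why the Kaplan-Meier estimate should sit beside it.
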